4 OBJECTIVES AND ENDPOINTS

OBJECTIVES	ENDPOINTS	JUSTIFICATION FOR ENDPOINTS
Primary		
To assess efficacy of daily mycophenolate mofetil (MMF) to attenuate immunogenicity to pegloticase.	Proportion achieving and maintaining serum urate ≤ 6 mg/dL through 12 weeks, compared to concurrent controls.	Serum urate ≤ 6 mg/dL is slightly below the urate solubility threshold and this threshold has been the accepted standard for nearly all modern gout trials. 23-26 If the serum urate goal is not maintained before or at the 12 week mark, it will be assumed that the participant has developed clinically relevant anti-pegloticase antibodies and they will receive no further infusions. This assumption and subsequent discontinuation of pegloticase is consistent with the protocol of large phase III randomized controlled trials and the product label.
To assess the incidence and types of adverse events/infusion reactions potentially associated with a dual therapy regimen of pegloticase and MMF.	Incidence and Type of Adverse Events (AEs), Serious Adverse Events (SAEs), and Participant withdrawals due to AEs, anaphylaxis, and Infusion Reactions (IRs)	Safety profile is important because of the addition of an immune modulatory agent (MMF) that has potential of causing serious AEs
Secondary		
To assess durability of immune modulation after discontinuation	Absolute change in serum urate from baseline to wk 24; week 12 to 24 Proportion of participants with serum urate < 6 mg/dL through week 24; week 12 to 24	Assess if the efficacy of the short course of MMF continues following discontinuation.
To identify and characterize pegloticase immune response by immunoglobulin	Anti-pegloticase antibody isotypes (IgG/IgM), specificity, and titers	We anticipate that the primary Ab produced will be IgM anti-pegloticase but some participants, who will likely be the non-

OBJECTIVES	ENDPOINTS	JUSTIFICATION FOR ENDPOINTS
		responders will produce
		both IgM and IgG
		antibodies at earlier onset
To assess patient reported outcomes	PROs using PROMIS and Gout Impact score	To assess impact of the
(PRO)		intervention on patient
		reported outcomes
Tertiary/Exploratory		
Not applicable		

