10.4.3 ANALYSIS OF THE PRIMARY SAFETY AND SECONDARY ENDPOINT(S)

The *primary safety aim* will examine the number of patients experiencing the event and the total number of events, their severity and relatedness to study drug will be summarized and all AEs and SAEs reported. Ascertaining safety outcomes will be mostly descriptive and the confidence intervals will remain wide for the proportion of responders, based on n = 32, but strong evidence to proceed with a larger trial is necessary.

The *secondary aims* are to: 1) Determine the 6 month durability of immune modulation after discontinuation of the short course of MMF by: a) assessing the absolute change in serum urate from baseline to Week 24, and Week 12 to Week 24, and b) determining the proportion of participants with serum urate ≤ 6 mg/dL through 24 weeks, and Week 12 to Week 24; 2) Identify and characterize the pegloticase immune response by immunoglobulin isotypes (IgG and IgM), specificities, and antibody titer, and 3) Examine patient reported outcomes (PROs) using the NIH supported Patient Reported Outcomes Measurement Information System (PROMIS)^{57,58} and Gout Impact Scale (GIS)^{59,60} instruments. For safety we will assess the incidence and types of adverse events / infusion reactions. The number of patients experiencing the event and the total number of events, their severity and relatedness to study drug will be summarized and all AEs and SAEs reported. Secondary endpoints including AEs across groups will be summarized using frequency and percentages. Continuous secondary outcome variables will be summarized using means with standard deviation (SD), and/or median and interquartile ranges (IQR) with 95% confidence intervals and compared by groups using t-tests or Wilcoxon tests as appropriate. Pegloticase Ab titers will be qualitatively analyzed for possible relationships with sUA lowering and the risk of IRs. Six month durability of response to MMF will be explored to assess if there is a threshold

^{*} Dash indicates a highly significant 2 tailed p-value using Fishers exact test

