These secondary outcome variables will be summarized using means with standard deviation, confidence intervals, and/or median and interquartile ranges, dependent on their distribution and plots of their response alone and in combination. Secondary endpoints will examine different definitions of sUA levels by plotting the initial values versus change values on the unbiased outcome results and time weighted averages; and 3) Examine PROs using the NIH supported Patient Reported Outcomes Measurement Information System (PROMIS)^{57,58} and Gout Impact Scale (GIS)^{59,60} instruments; these will use similar approaches of descriptive statistics, plots of PROs versus outcomes and correlations. The PROs will be summarized by change over time using means, 95% confidence intervals and compared between responder and non-responder status. We do not plan to control for the repeated testing using adjustments for multiple comparisons since this is a feasibility trial and since statistical significance is not the goal as it would be in a pivotal trial. The sample size is small and we see these secondary as well as primary analyses as descriptive. The p-values will be calculated, but will take the totality of the evidence into account in the interpretation. We considered using hierarchical testing such that each test would be done at the 0.05 level, but the low power argues that such could easily lead back to not considering secondary endpoints.

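### The only comparison specified for patient-reported outcomes is responders versus non-responders, a post-randomisation split that does not estimate the effect of MMF

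*Combined protocol and SAP*

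**What the plan says.** Section 4 lists the endpoint as "PROs using PROMIS and Gout Impact score". The justification column says it is there to show what the intervention does to these outcomes.

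Section 10.4.3 has two layers that bear on PROs.

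- **General rule.** After listing the secondary aims, with PROs as the third, it says continuous secondary variables will be summarised and "compared by groups using t-tests or Wilcoxon tests as appropriate". PROs are not excluded. The groups are not defined, although the sentence before reads "Secondary endpoints including AEs across groups will be summarized using frequency and percentages", which suggests treatment groups.
- **PRO text.** Under the third aim it says "these will use similar approaches of descriptive statistics, plots of PROs versus outcomes and correlations". It then plans to summarise how the PROs change, with means and intervals, and says they will be "compared between responder and non-responder status". No PRO sentence names the randomised arms, a main time point, a baseline score or a model.

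For the antibody and durability aims, the same section does name a treatment-group comparison, with two-group t-tests and regression.

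Section 8.1 classifies a participant as a non-responder after two consecutive serum urate values above 6 mg/dL.

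**The concern.** Responder status is the trial's efficacy outcome. It arises after treatment has started, and MMF is meant to change it. Splitting participants by it gives up the protection of randomisation: responders and non-responders may differ in disease burden, tolerance and time under observation, whatever arm they are in.

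The endpoint is meant to describe the impact of the intervention. If the responder contrast is reported as the PRO result, readers may take an association between urate control and well-being as evidence about MMF. A real MMF effect on PROs that does not act through response could go largely unseen.

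The timing of assessments adds to this. Under Section 8.1 and the Visit 17 reminder in Section 9, a discontinued participant has Visit 17 two weeks after stopping and then Visits 18 to 20, at which no PROs are listed. Change over time can therefore cover different periods in the two response groups.

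**Working it through.** **Inputs.** Arm sizes are 24 peg+MMF and 8 peg+PBO (Section 10.4.1). Planning response rates are 80% with MMF and 60% without (Section 10.2). The documents give no expected PRO effect, so effects are left as symbols.

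**The plan's own figure.** No sample size or effect is stated for PROs. The two rates are those behind the 82 per group in Section 10.2, which reproduces with the pooled-variance formula:

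[1.96 × √(2 × 0.7 × 0.3) + 0.8416 × √(0.6 × 0.4 + 0.8 × 0.2)]² / 0.2² = (1.270 + 0.532)² / 0.04 ≈ 81.2, rounded up to 82.

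**Step 1: expected make-up of the response groups.**

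| | MMF | Placebo | Total | MMF share |
|---|---|---|---|---|
| Responders | 0.8 × 24 = 19.2 | 0.6 × 8 = 4.8 | 24.0 | 19.2 / 24 = 0.80 |
| Non-responders | 0.2 × 24 = 4.8 | 0.4 × 8 = 3.2 | 8.0 | 4.8 / 8 = 0.60 |

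The group sizes match the arm sizes by coincidence. The people differ: 4.8 placebo participants are among the responders and 4.8 MMF participants among the non-responders.

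**Step 2: what each contrast shows.** Let d be an MMF effect on a PRO that is unrelated to response, and g the PRO gap between responders and non-responders within an arm.

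- Responder contrast = g + (0.80 − 0.60) × d = g + 0.2d
- Arm contrast = d + (0.80 − 0.60) × g = d + 0.2g

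The two values of 0.20 have different sources. The first is the difference in MMF share from Step 1. The second is the difference in response rates.

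**Step 3: special cases.**

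- Effect unrelated to response (g = 0): the arm contrast shows d and the responder contrast shows 0.2d.
- Effect only through response (d = 0): the arm contrast is 0.2g and the responder contrast is g, five times larger.
- No MMF effect at all (d = 0, equal response rates): the arm contrast is 0 and the responder contrast is still g.

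**Step 4: sensitivity of the 0.2 factor.** At equal rates, for example 60% in both arms, the MMF shares are 14.4/19.2 and 9.6/12.8, both 0.75, so the factor is 0. At an assumed 90% versus 58%, the shares are 21.6/26.24 = 0.823 and 2.4/5.76 = 0.417, so the factor is about 0.41.

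**Step 5: precision of the arm contrast.** For one visit with all 32 scores present, the 95% half-width is t(0.975, 30 df) × √(1/24 + 1/8) = 2.042 × 0.408 ≈ 0.83 SD.

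**The case against.** The strongest reply is that the arm comparison is already planned. PROs are a listed secondary aim, the general rule covers continuous secondary variables without exception, and the PRO sentences contain no word such as only or instead. An analyst could run both comparisons without contradiction. This stands in part. A reader might infer that PROs will not be compared between randomised arms at all, and the documents do not support that. But the general sentence leaves its groups undefined and fixes no PRO score, time point or baseline, and the specific sentence that follows names another contrast. Nothing makes the arm comparison the main PRO result.

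A reader might also infer that four fifths of any MMF effect on PROs would be lost. That holds only for an effect unrelated to response, at 80% versus 60%, and only if the responder contrast is the result relied on.

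Nor do the documents show that harm from MMF would be hidden. Tolerability is covered by the co-primary safety aim, with adverse events summarised across groups. The documents do not list the PROMIS-29 or GIS domains, so they cannot show whether these instruments would register gastrointestinal effects.

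Finally, Section 10.4.3 calls all the analyses descriptive, and the decision on a larger trial rests on urate response, antibody titres and safety (Sections 10.4.1 and 10.4.2). This limits the consequence. It does not make the named contrast suitable for the stated purpose, since p-values will be calculated and weighed with the rest of the evidence.

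**Conclusion.** The point holds. The one comparison specified for PROs is between groups formed after randomisation, and it does not answer the question for which Section 4 includes the endpoint. The general by-group rule softens this without resolving it.

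At the planning rates, the responder contrast carries about 0.2 of an MMF effect unrelated to response, and it can differ from zero with no MMF effect. The factor ranges from 0 at equal response rates to about 0.41 at an assumed 90% versus 58%. These figures assume additive effects and that all 32 participants have PRO scores. The actual PRO effect is unknown.

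This is worth correcting before the data are unblinded. It bears on how the PRO results are read, not on the decision about a larger trial.

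**What to change.** State in Section 10.4.3 that the main PRO analysis compares randomised arms in the mITT set, for PROMIS-29 and GIS, with 95% confidence intervals.

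- **Baseline.** Adjust for the Visit 1 score. Randomisation and dispensing occur at Visit 2, so the Visit 3 score, labelled baseline, is already post-randomisation.
- **Model.** Use all scheduled PRO visits, for example in a mixed model with estimates at Weeks 12 and 24. The section already plans PROC MIXED with participant random effects for serum urate.
- **Early failure.** Analyse the early Visit 17 PRO of a discontinued participant at its actual time, not as a Week 24 value. Add a sensitivity analysis for PROs missing after failure. At the planning rates, up to 0.2 × 24 = 4.8 MMF and 0.4 × 8 = 3.2 placebo participants could lack a true Week 12 or Week 24 score.
- **Schedule.** Reconcile Section 8.1 and the Visit 17 reminder with the Follow-up paragraph of Section 9, which says all data will be collected as scheduled after the study drug is stopped.
- **Responder contrast.** Keep it, labelled as a descriptive association that does not estimate an MMF effect.

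PROs are already collected at Visit 1 and through Visit 17, so no new data are needed. The cost is SAP wording and a little more analysis. The interval will be wide, with a half-width of about 0.83 SD before adjustment, and should be reported as such.

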10.4.4 BASELINE DESCRIPTIVE STATISTICS

Intervention groups will be compared on baseline characteristics and will include the following.

- Inclusion and Exclusion Criteria
- Demographics and Baseline Characteristics
- Medical History
- Disease History
- Medication History
- Laboratory values

Demographics will be summarized using descriptive statistics, by treatment group and site.

10.4.5 INTERIM ANALYSES

Not applicable for a pilot study of this nature. Safety findings that may prompt temporary suspension of enrollment and safety review are discussed in section 8.1.

10.4.6 SUB-GROUP ANALYSES

Not applicable for a pilot study of this nature

10.4.7 MISSING DATA AND OUTLIERS

We will perform imputation for the anticipated small number of missing outcomes, but as is now becoming commonly known, we expect the impact of such imputation to be minor. The imputation may be slightly different for different outcomes. For a given outcome, missing data from a visit missed that is flanked by available visits may allow for

averaging and multiple imputation based on the average of the flanking values. The utility of this approach will necessarily depend on the type of missing data and the pattern of the flanking values. In cases where imputation is deemed appropriate, PROC MI /PROC MIANALYZE (SAS Institute Inc., Cary, NC) will be used. We will generate five replicates of the event or outcome of interest and redo the assessments. For secondary and exploratory outcomes, we will use similar approaches. We will use propensity score matching (which reduces the cohort by any mismatches and thus is different than covariate adjustment) to assess the impact of the missingness mechanism. We will examine the sensitivity of the conclusions to any missingness found.

11 SUPPORTING DOCUMENTATION AND OPERATIONAL CONSIDERATIONS

11.1 REGULATORY, ETHICAL, AND STUDY OVERSIGHT CONSIDERATIONS

11.1.1 INFORMED CONSENT PROCESS

11.1.1.1 CONSENT/ASSENT AND OTHER INFORMATIONAL DOCUMENTS PROVIDED TO PARTICIPANTS

Consent forms describing in detail the study intervention, study procedures, and risks will be given to the participant and written documentation of informed consent is required prior to starting intervention/administering study intervention. The following consent materials are submitted with this protocol.

11.1.1.2 CONSENT PROCEDURES AND DOCUMENTATION

Informed consent is a process that is initiated prior to the individual's agreeing to participate in the study and continues throughout the individual's study participation. Participants will be asked to read and review the UAB IRB approved consent forms (see MOOP section 2.f). The investigator will explain the research study to the participant and answer any questions that may arise. A verbal explanation will be provided in terms suited to the participant's comprehension of the purposes, procedures, and potential risks of the study and of their rights as research participants. Participants will have the opportunity to carefully review the written consent form and ask questions prior to signing. The participants should have the opportunity to discuss the study with their family or surrogates or think about it prior to agreeing to participate.

The participant will sign the informed consent document prior to any procedures being done specifically for the study. Participants will be informed that participation is voluntary and that they may withdraw from the study at any time, without prejudice. A copy of the informed consent document will be given to the participants for their records. The informed consent process will be conducted and documented in the source document (including the date), and the form signed, before the participant undergoes any study-specific procedures. The rights and welfare of the participants will be protected by emphasizing to them that the quality of their medical care will not be adversely affected if they decline to participate in this study.

11.1.2 STUDY DISCONTINUATION AND CLOSURE

This study may be temporarily suspended or prematurely terminated if there is sufficient reasonable cause. Written notification, documenting the reason for study suspension or termination, will be provided by the suspending or terminating party to study participants, investigator, NIAMS, and regulatory authorities. If the study is prematurely terminated or suspended, the PI will promptly inform study participants, the IRBs, and NIAMS and will provide the reason(s) for the termination or suspension. Study participants will be contacted, as applicable, and be informed of changes to study visit schedule.

Circumstances that may warrant termination or suspension include, but are not limited to:

- Determination of unexpected, significant, or unacceptable risk to participants
- Demonstration of efficacy that would warrant stopping
- Insufficient compliance to protocol requirements
- Data that are not sufficiently complete and/or evaluable
- · Determination that the primary endpoint has been met
- Determination of futility

Study may resume once concerns about safety, protocol compliance, and data quality are addressed, and satisfy the NIAMS, IRBs, and/or FDA.

11.1.3 CONFIDENTIALITY AND PRIVACY

Participant confidentiality and privacy will be strictly held in trust by the participating investigators, their staff, and their interventions. This confidentiality is extended to cover testing of biological samples in addition to the clinical information relating to participants. Therefore, the study protocol, documentation, data, and all other information generated will be held in strict confidence. All research activities will be conducted in as private a setting as possible.

The study monitor, other authorized representatives of the NIAMS, representatives of the IRB, regulatory agencies or pharmaceutical company supplying study product may inspect all documents and records required to be maintained by the investigators, including but not limited to, medical records (office, clinic, or hospital) and pharmacy records for the participants in this study. The clinical study site will permit access to such records.

The study participant's contact information will be securely stored at each clinical site for internal use during the study. At the end of the study, all records will continue to be kept in a secure location for as long a period as dictated by the reviewing IRB, Institutional policies, or NIAMS requirements.

Study participant research data, which is for purposes of statistical analysis and scientific reporting, will be transmitted to and stored at the (DCC, based in the UAB Department of Biostatistics in the School of Public Health, directed by [name] (Co-Investigator). This will not include the participant's contact or identifying information. Rather, individual participants and their research data will be identified by a unique study identification number. The study data entry and study management systems used by clinical sites and by research staff will be secured and password protected. At the end of the study, all study databases will be archived at UAB.

11.1.4 FUTURE USE OF STORED SPECIMENS AND DATA

With the participant's approval and as approved by local Institutional Review Boards (IRBs), de-identified biological samples will be stored at the lab of [name], PhD at the University of Alabama at Birmingham. These samples could be used to for further research into the effects of MMF on pegloticase immunogenicity, its complications and other conditions for which individuals with gout are at increased risk, and to improve treatment. The [name] Lab will also be provided with a code-link that will allow linking the biological specimens with the phenotypic data from each participant, maintaining the blinding of the identity of the participant.

During the conduct of the study, an individual participant can choose to withdraw consent to have biological specimens stored for future research. When the study is completed, access to study data and/or samples will be reviewed and approved by the Coordinating Center at UAB, and provided through the [name] Lab.

11.1.6 SAFETY OVERSIGHT

In collaboration with NIAMS and KAI, we will convene a DSMB for additional monitoring of study procedures. The safety of the study participants is the highest priority for this project. The ability to make appropriate, sound scientific decisions regarding the outcome of each participant as early as possible is the top priority and as such, a process for the ongoing monitoring of results by independent scientists is important to maintain throughout the duration of the project. The DSMB will be comprised of 3 scientists who are independent of the study, the study investigators, and the University of Alabama at Birmingham and the University of Michigan for this clinical trial.

11.1.7 CLINICAL MONITORING

[name], MBA, CCRP, a member of the DCC at UAB, will conduct clinical site monitoring. Clinical monitoring will be conducted to ensure that the rights and well-being of trial participants are protected, that the reported trial data are accurate, complete, and verifiable, and that the conduct of the trial is in compliance with the currently approved protocol/amendment(s), with International Conference on Harmonization Good Clinical Practice (ICH GCP), and with applicable regulatory requirement(s).

Sites will be monitored within at least 4-6 weeks of enrolling their second participant. Subsequent visits will take place every 6 months, or in the event there is an identified need for a visit. Independent audits will be conducted by the DCC to ensure monitoring practices are performed consistently across all participating sites and that monitors are following the CMP.

Case report forms and de-identified study source documents (including informed consent) for the first participant at each site will be submitted to the via email at [contact] for review within 2 weeks of the baseline exam. Source documents will include: medical history, clinical notes, lab reports, informed consent process documentation, research lab worksheets, etc. Source documents will be checked against the eDES case report forms and the case report forms will be checked against the database tables. Printed laboratory reports and reports from the electronic medical record must include the date printed and signed by staff member printing the report. This will permit remote monitoring in a timely manner and can identify errors early in the data acquisition and entry process.

- 1. Monitoring visits will be conducted using the following guidelines:
 - a. Sites will be notified at least 30 days prior to the site visit.
 - b. 100% regulatory review, including informed consent review, will be conducted using a combination of files and onsite review.
 - c. Ideally, at least one study participant record per activated clinical trial will be reviewed per site during a single visit
 - The data of a site's first enrollment will be 100% reviewed by the monitor.
 - At least one study participant case review will be conducted, with no upper limit; more cases can be added at the discretion of the DCC and monitor.
 - d. The monitor will provide a preliminary report at the close of the monitoring visit.

- e. The monitor (or designated representative) is responsible for writing a formal report no more than 10 business days following the visit. This will allow members of the DCC to review reports prior to formal submission to sites.
- f. The monitoring visit report is sent initially to the DCC, and the study PI.
- g. The study PI and study statistician will review the monitoring reports and make recommendations to the Site PI and monitor within 2 weeks of receipt.
- h. It is the responsibility of the CCC to write a letter, and send it along with the report and any recommendations to the site PI of the institution being monitored, outlining any issues resulting from the monitoring visit. This will be done within one week of reviewing the monitoring report.
- i. If the actions and responses are straightforward with no major concerns, the CCC will send a letter of compliance and recommendation of approval of the monitoring report and response(s).
- j. The timeline for response will begin with a four week deadline. If further time is needed, the sanctioned institution may request (in writing) an extension and state the reason. If the institution in question is that of the study contact PI, the co-PI will be informed and issue the letter.

2. The Site PI responsibilities are:

- a. A reply to all issues addressed in monitoring report is due within 30 days of receipt of the monitoring review. This should be stipulated in the official letter. The letter should be sent via email notification.
- b. Serious issues may be referred to the DCC for further review. The DCC may decide to inform the DSMB.
- c. Once a site has responded to the requests in a timely manner, the DCC may either:
 - Send a formal closure letter stating that compliance has been met and close-out the monitoring review and follow-up.
 - Send a formal letter stating that compliance has not been met and the course of action that will follow;
 options may consist of any or all of the following:
 - Site visit and/or formal monitoring visit
 - Place the site on probation, with agreement of the CCC. The appropriate timeline to correct issues will be determined on a case-by-case basis depending upon the nature of the issue(s).
 - Require further training with a probationary period (to be determined)
 - Obtain recommendations from other groups, i.e., DSMB, sponsor, site IRBs and etc.
- d. Cases of severe non-compliance will be submitted to the CCC for recommendations that could result in:
 - Probation
 - Funding restrictions
 - A call to cease site enrollment
 - Report filed to the appropriate regulatory entities
 - Rejection of site status

Once a site is placed on probation, reinstatement can occur only with a formal letter signed by the study PI. In cases where non-compliance pertains to the institution of the Study PI ([name]), then a letter signed by the co-PI ([name]) would be sent.

In addition, Drs. [name] (U. Michigan) and [name], MPH (UAB) will serve as medical monitors for the study. Drs. [name] and [name] will be consulted on an *ad hoc* to answer questions from clinical investigators at UAB, UM, and from participating clinical sites. Their primary responsibilities include (but are not limited to):

- Providing medical leadership to sites by answering investigator questions about the protocol and the medical management of subject emergencies
- Providing input on clinical development plans, protocol design, and risk assessments
- Reviewing all study team deliverables, such as final narratives and clinical study reports
- Reviewing and analyzing safety and efficacy trends

